8.9 Return or Destruction of Study Drug / Medical Device

At the end of the intervention, the used material is sent back to Cort X Sensorics (Spaichingen, Germany).

9. STUDY ASSESSMENTS

9.1 Study flow chart / table of study procedures and assessments

1) Screening for	2) Enrollment and
suitable candidates	signing of informed
at Rehaklinik	consent if suitable
Bellikon	candidate

Phase 1 (Assessment of primary outcome, 7h)

	Day 1	Day 2	Day 7	Day 14	Day 21	Day 28	Day 31
Testing recepive fields (ca. 1h)	1x	1x	1x	1x	1x	1x	1x
Tester	А	А	А	В	А	В	A
Time of day	х	х	х	Х	х	х	х

9.2 Assessments of outcomes

9.2.1 Assessment of primary outcome

The primary measured outcome is the evolution/difference in size and position/movement of the detected receptive fields. This is done in the unit of cm^2 .

To record the data needed to compare the receptive fields is collected as follows:

- Day 1: detection of the receptive fields by one single tester at a self-selected time of day.
- Day 2: detection of the receptive fields at the same time of day as on day 1 by the same tester as on day 1.
- Day 7: detection of the receptive fields at the same time of day as on day 1 by the same tester as on day 1.
- Day 14: detection of the receptive fields at the same time of day as on day 1 by another tester as on day 1.
- Day 21: detection of the receptive fields at the same time of day as on day 1 by the same tester as on day 1.
- Day 28: detection of the receptive fields at the same time of day as on day 1 by the same tester as on day 14.
- Day 31: detection of the receptive fields at the same time of day as on day 1 by the same tester as on day 1.

The expression "same time of day" stands for:

-at maximum 1-hour difference in timing between the measurements.

-similar sleeping and dietary pattern 12 hours prior the measurement (assessed through a questionnaire).

The detection of the receptive fields is planned as follows:

- 1. performed by two specifically trained persons
- 2. performed through tactile stimulation of the skin surface with a brush (mild toothbrush or similar).
- 3. the receptive fields are determined through the dialogue with the participant. Here he can signal the presence of a receptive field with the word "Yes". Important in this setup is that the participant does not look at the inspected site or the tester.
- 4. the receptive fields are drawn on to the skin with a commercial eyeliner pencil.
- 5. the drawn receptive fields are photographed from different locations under standardized conditions (distance and angle).
- 6. this photo is imported in the program Photoshop (Adobe Photoshop Version 2017.1.1) where the respective area and position can be determined.

As a change in size is defined as a difference of more than 10% when comparing the same receptive field of two separate times.

We define as a change in position if the area of the two overlapping areas exceeds the area of the bigger of the two single areas by more than 20%. So, if the two areas overlap completely (even if different in size) we do not count it as a change in position.

As every meeting last approximatively one hour, we estimate a total duration of about 7 hours for this phase of the study.

9.2.2 Assessment of secondary outcomes

The Intra-/intertester reliability of the proposed detection method as secondary outcome is assessed by comparing the size and position of the detected receptive between two different testers. Here the sizes and positions are compared and the deviations calculated. The detection takes place as described in section 9.2.1.

The influence of the Phantom Stimulator on gait parameters and phantom sensations is assessed through a gait analysis (OPTOGait, Microgate S.r.I, Italy, 2010) and a self-made questionnair.

After the conclusion of the first descriptive part of the trial, the participants qualifying for the Phantom Stimulator are tested. These tests are performed in one single day.

This day is planned as follows:

- first (for familiarization): Walking for 1000 Steps with a step counter, questionnaire and 10 runs of gait analysis
- second: The Phantom Stimulator (Cort X Sensorics, Spaichingen, Germany) will be installed
- third: Participants will perform A or B in a randomized and balanced order:
 - A. walking with the functioning (ON) Phantom Stimulator (1000 steps), questionnaire and 10 runs of gait analysis
 - B. walking with the unfunctional (OFF) Phantom Stimulator (1000 steps), questionnaire and 10 runs of gait analysis

For gait analysis, subjects will be walking in maximally possible self-selected speed for 10 runs (both directions are analyzed).

The recorded parameters during the gait analysis are:

- Step width
- Step length
- Ground contact time
- Cadence
- Walking speed

The 1000 steps during the familiarization and testing phases are recorded/controlled through a pedometer (Omron Walking Style One 2.0, Mannheim, Germany).

The questionnaire evaluating the short-term effects of the Phantom Stimulator on phantom sensations addresses the existence of these sensations and their nature with a VAS from 0-10 and is performed directly after the 1000 steps (right before the gait analysis).

For this phase of the study we calculate approximatively 4 hours. The "Phantom Stimulator" is worn during approximatively 3 hours.

9.2.3 Assessment of other outcomes of interest

Not applicable.

9.2.4 Assessment of safety outcomes

9.2.4.1 Adverse events

In case of adverse events the event must be noted on the CRF. If the adverse event endangers the safety of the participant the testing must be stopped immediately.

In all cases the following information needs to be collected and recorded on the CRF: time of

onset, duration, action to be taken, relationship with study treatment.

9.2.4.2 *Laboratory parameters*

As there is no laboratory involved in this study, these parameters do not have to be assessed.

9.2.4.3 Vital signs

In this study, no vital parameters will be assessed as they are not of importance to the intervention. Further, as this study does not intend to change or affect any of these parameters, no assessment is necessary.

9.2.5 Assessments in participants who prematurely stop the study

After the recording of the reasons of premature withdrawal from the study (If there are any) and the rendering of the device (if in second part of the study), the participants do not receive any follow up procedures directly related to the intervention.

9.3 Procedures at each visit

9.3.1 Screening (until day 0)

- Screening done by the personnel of Rehaklinik Bellikon prior to the contact with the patients through the database of the clinic
- Afterwards an e-mail is sent to the included patients ([contact]) or they are contacted personally if stationary at the Rehaklinik Bellikon
- If the contacted patients show interest, a last interview is conducted to assess important inclusion and exclusion criteria (also pregnancy test) and if applicable sign the informed consent
- If they suit the study, they are scheduled for the meetings

9.3.2 Meeting 1 (day 1, 1h)

• Detection of the receptive fields by one single tester at a self-selected time of day (selected during scheduling in screening)

9.3.3 Meeting 2 (day 2, 1h)

• Detection of the receptive fields at the same time of day as on day 1 by the same tester as on day 1

9.3.4 Meeting 3 (day 7, 1h)

• Detection of the receptive fields at the same time of day as on day 1 by the same tester as on day 1

9.3.5 Meeting 4 (day 14, 1h)

• Detection of the receptive fields at the same time of day as on day 1 by another tester as on day 1

9.3.6 Meeting 5 (day 21, 1h)

• Detection of the receptive fields at the same time of day as on day 1 by the same tester as on day 1

9.3.7 Meeting 6 (day 28, 1h)

• detection of the receptive fields at the same time of day as on day 1 by the same tester as on day 14

9.3.8 Meeting 7 (day 31, 1h)

• detection of the receptive fields at the same time of day as on day 1 by the same tester as on day 1

9.3.9 Meeting 8 (second part of the study, done in 1 single half-day, 4h)

- **Phase 1:** Familiarization (1000 steps, questionnaire and gait analysis)
- **Phase 2:** Fitting of System and randomization
- Phase 3: AB or BA
 - A. walking with the functioning (ON) Phantom Stimulator (1000 steps), questionnaire and 10 runs of gait analysis
 - B. walking with the unfunctional (OFF) Phantom Stimulator (1000 steps), questionnaire and 10 runs of gait analysis

10. SAFETY

10.1 Medical Device Category A studies

10.1.1 Definition and Assessment of safety related events

- Health hazards that require measures
- Findings in the trial that may affect the safety of study participants and which require preventive or corrective measures intended to protect the health and safety of study participants

Findings which require preventive or corrective measures:

- All of the above
- Malfunctioning of the device
- Skin irritations related to the electrodes
- Pregnancies
- Implanted devices (pacemaker or defibrillator)

10.1.2 Reporting of Safety related events

Reporting to Sponsor-Investigator:

• Health hazard that require measures are reported to the Sponsor-Investigator within 24 hours upon becoming aware of the event:

Pregnancies:

• Reporting of pregnancies is mandatory within 24 hours to the investigators at Rehaklinik Bellikon. This event has the exclusion from the second part of the study as consequence.

Reporting to Authorities:

- In Category A studies it is the Investigator's responsibility to report to the local Ethics Committee
- Health hazards that require measures within 2 days

11. STATISTICAL METHODS

11.1 Hypothesis

Null Hypothesis:

- 1) Receptive fields do not change in position and size over the various measured time intervals
- 2) The intra-/intertester reliability concerning the proposed detection system is good and therefore no difference in detection are seen
- 3) The stimulating device has no effect on the participants performing a gait analysis (selected parameters) and answering a questionnaire regarding phantom sensations

Alternative Hypothesis:

- 1) The position and size of the detected receptive fields changes significantly over the various measured time intervals
- 2) The intra-/intertester reliability concerning the proposed detection system is imperfect and therefore difference in detection can be seen
- The stimulating device has a significant effect on the participants performing a gait analysis (selected parameters) and answering a questionnaire regarding phantom sensations

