	(Streuung) between	similar population sub	ogroups (chronic pain		
	patients) is of 0.27%.				
	Therefore, the effect size is d = 1.11 with μ_i = 0.3 and SD = 0.27.				
	We set the significant	ce level at 5% and the p	power at 0.8.		
	Using the paired t-tes	t these values originate	e the following N's:		
	μ _i	d	Ν		
	0.25	0.93	40		
	0.3 1.11 28				
	0.35 1.23 24				
	As we assume a dropout rate of 10% we aim at 31 Participants for				
	the duration of this st	udy.			
Study Duration:	For each subject, the	study lasts about 5 to 6	6 weeks.		
Study Schedule:	First subject: 24.10.2	017			
	Last subject: 08.05.2018				
Investigator(s):	[name],				
	Sportmedizin und Re	habilitation			
	[name]				
Study Centre(s):	Rehaklinik Bellikon				
	[name]				

Statistical	ical Statistical Analysis:				
Considerations:	The statistical analy and "Excel".	ysis is performed wi	th the program "R"		
	For the primary outcome, the pictures are evaluated for size and position with the computer program "Photoshop". We define a change in size if a difference of more than 10% is detected in comparing a receptive field of two measurements. We define a change in position if the summed area of the two overlapping receptive fields exceeds the area of the bigger of the two single receptive fields by more than 20%. So, if the two receptive fields overlap completely (even if different in size) we do not count it as a change in position (only change in size).				
	For the secondary parameters of 10 rur compared between th	outcomes; a mean fo ns of gait analysis is c ne two randomized proto	or every one of the reated. These data is ocols (A and B).		
	All the results are tre 0.05 is achieved.	ated as significant if th	e significance level of		
	Power Analysis/Sam	nple size:			
	As this study is a first in this field (Pilot), regarding literature is not present and different assumptions (professional guesses) must be made.				

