11.2 Determination of Sample Size

As this study is a first in this field (Pilot), regarding literature is not present and different assumptions (professional guesses) must be made.

We define a change in size of the receptive field if over the 31 days the size change is of more than 10%.

We anticipate a change in size and position of 30% of the measured receptive fields between day 1 and 31 to be clinically significant for the purposes of our and further studies. In this case significant means that the attached electrodes at day 1 would not be touching the receptive field anymore at day 31.

From previous studies concerning the two-point discrimination (Catley M. J. (2014)) we know that the standard deviation (Streuung) between similar population subgroups (chronic pain patients) is of 0.27%.

Therefore, the effect size is d = 1.11 with $\mu_i = 0.3$ and SD = 0.27.

We set the significance level at 5% and the power at 0.8.

_	-	_
μi	d	Ν
0.25	0.93	40
0.3	1.11	28
0.35	1.23	24

Using the paired t-test these values originate the following N's:

As we assume a dropout rate of 10% we aim at 31 Participants for the duration of this study.

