11.4.3 Secondary Analyses

A secondary analysis concerning the inter- and intratester reliability is performed by the principal investigators ([name], [name]) at the end of the first part of the study (day 31). Here the days 1 and 2 are compared for intertester reliability and the days 28 and 31 are compared for the intratester reliability.

The secondary analysis concerning the intervention period (single day after day 31) is as well performed by the principal investigators ([name], [name]) after completion of the last gait analysis. Here the recorded gait parameters as well as the questionnaires are evaluated on changes originating between randomization A and B.

In both cases graphs and tables will be generated showing the mean, standard deviation, change as well as all single values of the participants.

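### Hypothesis 2 makes good reliability the null hypothesis, and the plan gives no agreement measure or acceptance limit, so absence of a significant difference could stand as 'good' reliability

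*Combined protocol and SAP*

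**What the plan says.** Section 11.1 lists as null hypothesis 2: "The intra-/intertester reliability concerning the proposed detection system is good and therefore no difference in detection are seen". The matching alternative is: "The intra-/intertester reliability concerning the proposed detection system is imperfect and therefore difference in detection can be seen". The synopsis (Statistical Considerations) treats every result as significant when the 0.05 level is reached, and section 11.2 adds "We set the significance level at 5% and the power at 0.8".

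The analysis text for reliability is descriptive. Section 9.2.2 says "Here the sizes and positions are compared and the deviations calculated". Section 11.4.3 compares one pair of days for each type of reliability and then says "In both cases graphs and tables will be generated showing the mean, standard deviation, change as well as all single values of the participants". The data sheet in 11.4.1 records size and percentage overlap for those pairs, with one sheet for every detected field.

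No section gives an intraclass correlation (ICC), limits of agreement, a measurement error, an equivalence margin or an acceptance limit. The 10% size rule and the 20% position rule in 9.2.1 define a change in a field. They are not offered as limits of acceptable reliability.

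**The concern.** Reliability of the detection method is a stated aim: the synopsis counts it among the primary outcomes, sections 4.3 and 5.2 list it as secondary, and section 6.2.3 cites it as a way of minimising bias. A claim that a study sets out to support should carry the burden of proof. Here it is the default, kept unless the data contradict it.

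A test of the mean difference is also the wrong instrument. It responds to systematic bias between two mappings. Random disagreement in field size, up in some participants and down in others, averages towards zero and does not move it. The statistic that would show random disagreement is an agreement measure with a limit, and none is planned.

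What is at stake is the interpretation of the main results. A field counts as changed in size when it differs by more than 10%. If repeat mapping alone produces differences of that order, true change cannot be told from mapping error, and the only inferential statement about mapping error is the reversed hypothesis. The problem is independent of which days are paired and of which comparison is labelled intra- or intertester. It remains after both are settled.

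**Working it through.** **The plan's own figure.** There is none for reliability. The only sample size, in 11.2, is for hypothesis 1 (change from day 1 to day 31): d = 1.11, two-sided 5%, power 0.8, N = 28, raised to 31 for dropout. The 28 reproduces as the total of a two-sided two-sample t-test (14 per group); the paired t-test named there would need 9. That is a separate matter. Here 28 serves only as the number of pairs, taking one field per participant.

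**Assumptions.** The documents give no SD or bias for repeat mappings, so ranges are shown. Differences between two mappings, as a fraction of field size, are taken as normal with SD 20% to 40%. The value 27% is included because 11.2 uses 0.27, although that figure is borrowed from two-point discrimination. The test is a two-sided paired t-test at 0.05, the only test the documents name.

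**Step 1. Random error only, mean difference 0.** The null of no mean difference is true, so the test is non-significant with probability 1 − 0.05 = 95% for any SD and any n. A 20,000-run simulation gave 94.7% to 95.3% for true ICCs of 0.95, 0.90, 0.75, 0.50, 0.20 and 0, at n=10 and n=28.

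The share of pairs differing by more than 10% is 2 × [1 − Φ(0.10/SD)]:

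- SD 20%: 2 × [1 − Φ(0.500)] = 62%
- SD 30%: 2 × [1 − Φ(0.333)] = 74%
- SD 40%: 2 × [1 − Φ(0.250)] = 80%

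**Step 2. A true systematic difference of 10% between mappings.** The t statistic is noncentral t with n − 1 degrees of freedom and noncentrality δ = 0.10 × √n / SD. 'No difference' is kept when |t| is below the critical value, which is 2.052 for n=28.

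| SD of differences | δ at n=28 | Kept, n=28 | Kept, n=20 | Kept, n=10 |
|---|---|---|---|---|
| 20% | 2.65 | 28% | 44% | 71% |
| 27% | 1.96 | 53% | 65% | 82% |
| 30% | 1.76 | 60% | 71% | 84% |
| 40% | 1.32 | 75% | 81% | 89% |

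With a real bias, 'good' is kept more often as noise rises and as the sample shrinks.

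**Step 3. A rule the right way round.** Suppose 'good' requires the lower 95% bound of a one-way ICC to reach 0.75 (an assumed value). The pass rates are:

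| True ICC | n=28 | n=10 |
|---|---|---|
| 0.95 | 99% | 72% |
| 0.90 | 73% | 31% |
| 0.85 | 31% | 13% |
| 0.75 | 2.5% | 2.5% |
| 0.50 | <0.1% | 0.1% |

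Poorer agreement now makes passing harder, and for a method truly above the bound a smaller sample does too.

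**The case against.** The strongest reply is that the decision rule is inferred. No test is named for reliability; the paired t-test appears only in the sample-size section, for another question. The 0.05 rule says when a result is significant, not what a non-significant one proves. The reporting in 11.4.3 is descriptive, and the SD and single values would let a reader see the spread and derive limits of agreement. All of this stands, and it is why the figures above are conditional. It does not remove the fault: the descriptive output comes with no criterion, so the reversed pair in 11.1 is the only stated basis for a conclusion.

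Three stronger readings are tempting, and the documents do not support them.

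- A reader might infer that random error is invisible throughout. That is true of a mean-difference test on size, but not of the planned output, nor of position. Overlap is unsigned, so displacement in any direction lowers it and errors do not cancel.
- A reader might infer that a noisier method or smaller study always passes more easily. That holds only with a non-zero systematic difference. With zero bias the rate stays at 95%.
- A reader might infer that every size and position result depends on accepting null 2. Section 11.4.2 contains no such gate. Mapping error affects interpretation, not whether the primary analysis proceeds.

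One could also apply the 10% change rule to the reliability pairs as a criterion. The plan does not say that it does so.

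**Conclusion.** Wrong as written. Hypothesis 2 puts good reliability in the null, and no agreement measure or acceptance limit elsewhere in the plan corrects it. The plan does not say that non-significance will be reported as proof; the point is that its only inferential framework would allow that.

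Used in that way for field size, the framework does not distinguish a method with no reliability from an excellent one when error is purely random. With a 10% bias at n=28 it misses the bias in roughly a quarter to three quarters of studies over the SD range considered. These sizes rest on assumed SDs and bias, normal differences, a paired t-test, and one field per participant. The direction of the fault does not depend on them: a non-significant difference cannot establish agreement.

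**What to change.** In 11.1, delete the null and alternative for hypothesis 2 and state reliability as an estimation aim. In 11.4.3, specify:

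- For size: an ICC for absolute agreement, and Bland-Altman limits on the log-area ratio, each with a 95% confidence interval.
- For position: the distribution of percentage overlap (mean or median, and a lower percentile) with a 95% confidence interval. Bland-Altman limits do not suit overlap, which is already a single value per pair of mappings.
- Several fields per participant: a mixed model, or a bootstrap that resamples participants.
- The criterion for calling reliability good, fixed before the data are seen; for example, a lower 95% bound of the ICC at a value the sponsor chooses.
- A sentence that a non-significant difference is not evidence of reliability.

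The cost is a few lines of text and somewhat more analysis on data already planned; study conduct does not change. The downside is that 'good' becomes harder to claim. With an assumed bound of 0.75 and n=28, a method with a true ICC of 0.90 would pass about 73% of the time and one of 0.85 about 31%, so the sponsor should choose the bound knowing this.

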5. STUDY OUTCOMES

5.1 Primary Outcome

The primary measured outcome is the evolution/difference in size and position/movement of the detected receptive fields. This is done in the unit of cm^2 .

This is done comparing size and position of the same receptive fields between day 1, 2, 7, 14, 21, 28 and 31 of the study.

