11.4.2 Primary Analysis

At the end of the 31-day period making up the first part of the study, the datasets concerning the receptive fields are evaluated by the principal investigators ([name], [name]).

Here, next to the numerical tables exhibiting the monitored changes in size and position of the receptive fields, a graph will be made explaining the occurrence of these fields in relation to the time since the amputation occurred.

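### No analysis is assigned to hypothesis 1, and the only test the plan names addresses mean signed change in size, while the plan defines change field by field and without sign

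*Combined protocol and SAP*

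**What the plan says.** Section 5.1: "The primary measured outcome is the evolution/difference in size and position/movement of the detected receptive fields", recorded in cm² and compared over days 1, 2, 7, 14, 21, 28 and 31.

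Section 11.1 gives the null as "Receptive fields do not change in position and size over the various measured time intervals" and the alternative as "The position and size of the detected receptive fields changes significantly over the various measured time intervals". Neither has a direction.

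Section 9.2.1 defines change for a single field. Size has changed if two measurements differ by more than 10%, up or down. Position has changed if the joint area of the two outlines exceeds the larger outline by more than 20%.

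Section 11.2 sizes the study: "We set the significance level at 5% and the power at 0.8", and "Using the paired t-test these values originate the following N's". The inputs are a mean of 0.3 and an SD of 0.27. The synopsis adds a general 0.05 significance rule for all results.

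Section 11.4.2, the primary analysis, offers "numerical tables exhibiting the monitored changes in size and position of the receptive fields" and a graph of field occurrence against time since amputation. It names no test. Section 6.1 calls this part of the study purely descriptive.

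**The concern.** The plan has a hypothesis, an alpha, a power and a per-field definition of change, but nothing joins them. An analyst who has to say whether null hypothesis 1 is rejected finds one named test. Applied to field size, it asks whether the average field grew or shrank. The hypothesis asks whether fields change at all.

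The two questions can have opposite answers. Fields that grow and fields that shrink offset each other in a signed mean, although each counts as changed under section 9.2.1. Section 11.2 makes the practical issue plain: would electrodes placed on day 1 still lie on the field at day 31? One field's growth does nothing to offset another field's shrinkage. At stake is a formal statement on the primary hypothesis that disagrees with the table printed beside it.

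**Working it through.** **1. The plan's own figure.** d = 0.30/0.27 = 1.11. At two-sided 5% and 80% power, the table's N of 40, 28 and 24 (d = 0.93, 1.11, 1.23) are the totals for a t-test of two independent groups. A paired t-test with d as the standardised difference needs 12, 9 and 8. Then 28 × 1.1 = 30.8, hence 31. The mislabelled test is a separate matter. I use n = 28, one field per participant.

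**2. What the paired test targets.** With D = area at day 31 minus area at day 1 (or the relative change), t = mean(D) / (SD(D)/√n), and the null is mean(D) = 0. The plan's rule is |A31/A1 − 1| > 0.10. If 14 fields grow by 30% and 14 shrink by 30%, mean relative change is 0, t = 0 and p = 1.0. Yet 28 of 28 fields have changed (exact 95% CI 87.7% to 100%).

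**3. With retest noise.** Assumed: +30% or −30% with equal chance, SD of the log ratio from retest 0.10, lognormal baseline areas with median 10 cm².
- Growing fields past the rule: Φ((ln 1.3 − ln 1.1)/0.10) = Φ((0.262 − 0.095)/0.10) = Φ(1.67) = 0.953.
- Shrinking fields past the rule: Φ((ln 0.9 − ln 0.7)/0.10) = Φ((−0.105 + 0.357)/0.10) = Φ(2.51) = 0.994.
- Average: 0.97.
- Simulated rejection by the paired t-test: 4% to 5% on cm². On relative change with noise SD 0.05 it is 5.1%. Both are about the false-positive rate.

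**4. Dependence on balance** (n = 28, relative scale).

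| Scenario | Fields past 10% | Rejection |
|---|---|---|
| ±30%, 50/50, noise SD 0.05 | about 100% | 5.1% |
| Normal, mean 0, SD 0.27 | 71% | 5.1% |
| ±30%, 60/40 | 100% | 15% |
| ±30%, 70/30 | 100% | 53% |
| ±30%, 80/20 | 100% | 91% |
| Normal, mean 0.3, SD 0.27 (planning case) | 84% | >99.9% |

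**5. The reverse mismatch.** A shift with mean 5% and SD 5% is rejected in 99.9% of studies, although only (1 − Φ(1)) + Φ(−3) = 0.159 + 0.001 = 16% of fields pass the 10% rule.

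**6. Position.** The overlap measure has no sign, so nothing cancels. What is missing there is any stated analysis.

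**7. What noise does to the share of changed fields.** With no true change, the share past the 10% rule is [1 − Φ(ln 1.1/s)] + Φ(ln 0.9/s).
- s = 0.10: 0.170 + 0.146 = 32%.
- s = 0.25: 0.352 + 0.337 = 69%.

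Comparing the day-31 share with 30% could therefore be satisfied by measurement error alone.

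**8. Which summary detects what.** A paired comparison of spread (Pitman-Morgan on log ratios, day 31 against day 2) rejects in essentially 100% of studies in step 3, but in only about 5% when all fields shift equally. The signed mean does the opposite. Both are needed.

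**The case against.** The strongest reply is that the plan never says it will use this test on the primary outcome. The paired t-test appears only in sample-size text. Its use on signed cm² would have to be assembled from section 5.1 (the unit) and section 11.2 (the test, on a relative scale). Part 1 is described as descriptive, section 11.4.1 provides a sheet for every detected field, and section 11.4.2 tabulates the changes, so growth and shrinkage would both be visible. All of that stands.

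A reader might infer that the plan will conclude there is no change when nearly every field has changed. The documents do not support this: no section says a non-significant result would be reported that way. The loss also needs near-balanced growth and shrinkage (step 4), and the documents say nothing about direction. Under the plan's own planning case the test would almost always reject.

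A reader might also infer that working in cm² costs serious power. With a uniform 15% shrinkage and retest log-SD 0.25, power on cm² is 84%, 60% and 52% for field-size log-SDs of 0.5, 1.0 and 1.2, against about 91% on log ratios. Those spreads are assumptions, since the documents give none. At the plan's own 30% change the figures are 99.9%, 97% and 93%, all above the planned 80%. This is a reason to prefer log ratios, not a defect by itself.

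The descriptive label does not dispose of the point. Sections 11.1 and 11.2 and the synopsis set hypotheses, alpha, power and a significance rule. If the t-test is not the analysis, hypothesis 1 has none, and the same text needs writing.

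**Conclusion.** The concern holds in limited form. Hypothesis 1 is non-directional, change is defined per field without sign, and the only test named addresses a signed mean. For size, using that test could leave rejection at about 5% while about 97% of fields pass the 10% rule. That figure rests on n = 28, one field per participant, balanced ±30% changes and retest log-SD 0.10, none of which the documents establish as likely. Rejection rises to 53% at a 70/30 split and 91% at 80/20. Position is not exposed to cancellation. The tables would still show the changes, so the risk is a formal conclusion at odds with the descriptive results, not a demonstrated wrong answer.

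**What to change.** In sections 11.1 and 11.4.2:

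- Analyse size as log(area at day t / area at day 1). For each interval report the signed mean log ratio (direction) and its SD or median absolute value (magnitude). Neither replaces the other.
- Judge magnitude at day 31 against the day 1 to day 2 comparison. The schedule has tester A on days 1, 2 and 31, so day 2 is a same-tester retest, although section 11.4.3 labels that pair intertester; correct the label. Any true change within one day is counted as noise, which makes the benchmark conservative.
- Report the share of fields classed as changed in size, and separately in position, at day 31 with a 95% CI, next to the same share at day 2. Do not judge it against 30% alone: noise can produce that figure, and section 11.2 leaves open whether 30% is an amount of change or a share of fields. Precision is modest: 8 of 28 gives an exact interval of 13.2% to 48.7%.
- Allow for several fields per participant, for example by resampling participants for the intervals.
- State that the paired t-test does not decide hypothesis 1.

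The cost is SAP wording and a few lines of R, with no new data. The downside is that part of what now counts as change will be attributed to measurement error.
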